10.9. Risks associated with privacy/loss of confidentiality (Data Security): Security of user information is of paramount importance to us. Research personnel will not contact any person without appropriate written release of information. All information collected will be kept in password-protected, HIPAA-compliant computers, secured using the best available methods. Information collected during the telephone screening will be discarded in cases when subject is not eligible for a screening in person. Research records will be kept as confidential as possible. Only a code number will identify subject research records. The code number will not be based on any information that could be used to identify subjects (for example, social security number, initials, birth date, etc.). The master list linking names to code numbers will be kept separately from the research data. This master list, as well as all the other research information will be kept in locked files at all times, in [name] /[name] laboratory. Subjects' identity will not be revealed in any reports or publications resulting from this study. Only authorized persons will have access to the information gathered in this study. As part of the study procedures, some

information about subject's participation will become part of their CMHC medical record. If a subject does not already have a medical record at CMHC, one will be made for their visit. Moreover, if a subject has been a patient at CMHC at any time, his or her previous medical records of other visits or admissions will become available to the researchers and to the staff of the CMHC, as part of the screening, or when the information collected for this research is added into their medical record. Information will be stored as per HIPAA guidelines. All staff has been trained in accordance with HIPAA regulations. Information will not be dispensed to anyone outside of this research project (e.g. , Yale HIC, CMHC, Yale Magnetic Resonance Research Center, and Yale PET Imaging Center) without prior written authorization from the subject. If we see or are told that a child is being abused or neglected or that there is a risk of harm to subject or others, we will disclose this information to the proper authorities. As part of the video (e.g., Skype or Facetime) conference call, subjects will not need to disclose any information about them given that principal investigator will be able to confirm their identity through the camera.

Procedures to minimize risks will be the same for subjects with ADHD. However; there will be no concerns/risks related with Skype or Facetime interview as this will not be required for them.

11. Data and Safety Monitoring Plan: Include an appropriate Data and Safety Monitoring Plan (DSMP) based on the investigator's risk assessment stated below. (Note: the HIC will make the final determination of the risk to subjects.) For more information, see the Instructions, page 24.

- a. What is the investigator's assessment of the overall risk level for subjects participating in this study?
Moderate risk
- b. If children are involved, what is the investigator's assessment of the overall risk level for the children participating in this study?
- c. Include an appropriate Data and Safety Monitoring Plan. Examples of DSMPs are available here <http://www.yale.edu/hrpp/forms-templates/biomedical.html> for
 - i. Minimal risk
 - ii. Greater than minimal
- d. For multi-site studies for which the Yale PI serves as the lead investigator:
 - i. How will adverse events and unanticipated problems involving risks to subjects or others be reported, reviewed and managed?
 - ii. What provisions are in place for management of interim results?
 - iii. What will the multi-site process be for protocol modifications?

1. Personnel responsible for the safety review and its frequency:

The principal investigator will be responsible for monitoring the data, assuring protocol compliance, and conducting the safety reviews in real time (e.g., on a weekly or bi-weekly basis as part of the Yale Cocaine Clinic rounds). During the review process, the principal investigator

will evaluate whether the study should continue unchanged, require modification/amendment, or be close to enrollment. Either the principal investigator or the IRB have the authority to stop/suspend the study or require modifications.

2. The risks associated with the current study are deemed moderate for the following reasons:

We do not view the risks associated with the [¹¹C]-PHNO PET, and/or medication administration component as minimal. Although we have assessed the proposed study as one of moderate risk, the potential exists for anticipated and/or unanticipated adverse events, serious or otherwise, to occur since it is not possible to predict with certainty the absolute risk in any given individual or in advance of first-hand experience with the proposed study methods. Therefore, we provide a plan for monitoring the data and safety of the proposed study as follows:

3. Attribution of Adverse Events:

Adverse events will be monitored for each subject participating in the study and attributed to the study procedures / design by [name], MD, PhD / [name], MD according to the following categories:

- a) Definite: Adverse event is clearly related to investigational procedures(s)/agent(s).
- b) Probable: Adverse event is likely related to investigational procedures(s)/agent(s).
- c) Possible: Adverse event may be related to investigational procedures(s)/agent(s).
- d) Unlikely: Adverse event is likely not to be related to the investigational procedures(s)/agent(s).
- e) Unrelated: Adverse event is clearly not related to investigational procedures(s)/agent(s).

4. Plan for Grading Adverse Events:

The following scale will be used in grading the severity of adverse events noted during the study:

- A. Mild adverse event
- B. Moderate adverse event
- C. Severe adverse event

5. Plan for Determining Seriousness of Adverse Events:

Serious Adverse Events: In addition to grading the adverse event, the PI will determine whether the adverse event meets the criteria for a Serious Adverse Event (SAE). An adverse event is considered serious if it:

- 1) is life-threatening OR
- 2) results in in-patient hospitalization or prolongation of existing hospitalization OR
- 3) results in persistent or significant disability or incapacity OR
- 4) results in a congenital anomaly or birth defect OR
- 5) results in death OR
- 6) based upon appropriate medical judgment, may jeopardize the subject's health and may require medical or surgical intervention to prevent one of the other outcomes listed in this definition, OR
- 7) adversely affects the risk/benefit ratio of the study

An adverse event may be graded as severe but still not meet the criteria for a Serious Adverse Event. Similarly, an adverse event may be graded as moderate but still meet the criteria for an SAE. It is important for the PI to consider the grade of the event as well as its "seriousness" when determining whether reporting to the HIC is necessary.

6. Plan for reporting Reportable Adverse Events and other unanticipated problems involving risks to subjects or others to the IRB

The principal investigator will report the following types of events to the HIC and the funding agency: a) serious AND unanticipated AND possibly, probably or definitely related events; b) anticipated adverse events occurring with a greater frequency than expected; and c) other unanticipated problems involving risks to subjects or others.

These adverse events or unanticipated problems involving risks to subjects or others will be reported to the HIC within 24-48 hours of it becoming known to the investigator, using the appropriate forms found on the website.

7. Plan for reporting adverse events to co-investigators on the study, as appropriate the protocol's research monitor(s), e.g., industrial sponsor, Yale Cancer Center Data and Safety Monitoring Committee (DSMC), Protocol Review Committee (PRC), DSMBs, study sponsors, funding and regulatory agencies, and regulatory and decision-making bodies.

For the current study, the following individuals, funding, and/or regulatory agencies will be notified (choose those that apply):

- All Co-Investigators listed on the protocol.
- Yale Cancer Center Data and Safety Monitoring Committee (DSMC)
- National Institutes of Health^[1]

- Yale University Radioactive Drug Research Committee (YU RDRC), if applicable
- Food and Drug Administration (Yale PET Center Sponsored IND #134,138), if applicable
- Medical Research Foundation (Grant _____)
- The Brain and Behavior Research Foundation

The principal investigator [name], PhD will also conduct a review of all adverse events upon completion of every study subject. The principal investigator will evaluate the frequency and severity of the adverse events and determine if modifications to the protocol or consent form are required. DSMP and plan for reporting adverse events will be the same for ADHD subjects.

12. Statistical Considerations: Describe the statistical analyses that support the study design.

Data Analysis: The PET image sets are aligned and re-sliced to yield images in the same planes and spatial system as the MRI images using AAL template. A number of modeling approaches will be taken to quantitate binding potentials (BP_{ND}). Initially, the primary focus will be on reference region approaches, specifically the Simplified Reference Tissue Models (SRTM); i.e., time-activity curves will be fitted with the Simplified reference tissue model to extract binding potentials (BP_{ND}) in various brain regions.

Data Analyses: The primary outcome will be non-displaceable tracer binding potentials ($BP_{ND} = V_T - V_{REF} / V_{REF}$), which are linearly proportional to the density of available $D_{2/3}$ Rs, computed using a simplified reference tissue model (SRTM) utilizing the cerebellum as a reference region. This method has been previously validated. PET data will be reconstructed into images at Yale PET Center with all standard corrections using the appropriate reconstruction protocols and filters. All PET data will be reconstructed with an iterative reconstruction algorithm, MOLAR, designed specifically for the HRRT. MOLAR incorporates attenuation, scatter and deadtime, and subject-motion (detected by the Vicra system), into the forward projection model for the scanner. Emission images are binned into equal frame times (typically 3 minutes). Following image reconstruction, an early summed image (0-12 min) will be registered to the subject's MR image, which will be registered to an MR template so PET can be transformed to a standard (MNI) space. HYPR filtering will be applied to all emission data before analysis. Regions of interest will be the caudate, putamen, ventral striatum (VST), and substantia nigra / ventral tegmental area (SN/VTA). We will perform within-subject comparisons of the relative change in BP_{ND} elicited by calcitriol + Amp vs. placebo + Amp (ΔBP_{ND}), using appropriate parametric (paired t-) or non-parametric (Wilcoxon signed-rank test) tests. Although the proposed sample will enable detection of significant differences of moderate effect sizes ($d' = 0.59$) with a power of 0.8 and two-tailed alpha of 0.05, the sample will, at a minimum, provide estimates of effect size/power upon which future larger scales studies may be based. This effect size is congruent with preclinical work (Cass, Peters et al. 2012) and with clinical [^{11}C]-(+)-PHNO and [^{11}C]

Raclopride studies (Shotbolt, Tziortzi et al. 2012). In secondary analyses, we will examine correlations (Pearson's) between cognitive (e.g., CPT-IP and PRLT), psychomotor (e.g., eye blink rate), and subjective (e.g., DEQ and simplified version of the amphetamine interview rating scale) measurements and neuroimaging outcomes/stimulant effects.

Statistical analyses will be the same for subjects with ADHD.

SECTION VI: RESEARCH INVOLVING DRUGS, BIOLOGICS, RADIOTRACERS, PLACEBOS AND DEVICES

If this section (or one of its parts, A or B) is not applicable, state N/A and delete the rest of the section.

A. DRUGS, BIOLOGICS and RADIOTRACERS

1. Identification of Drug, Biologic or Radiotracer: What is (are) the **name(s)** of the drug(s) biologic(s) or radiotracer(s) being used? Identify whether FDA approval has been granted and for what indication(s).

Radiotracer ([¹¹C]-PHNO): At the Yale PET center, we have characterized and applied an improved agonist radiotracer for the D2/3 receptor, [¹¹C]-PHNO, demonstrating its excellent test-retest variability in striatum (Gallezot et al., 2014b) and its greater sensitivity to Amp-induced DA release relative to traditional antagonist ligands (i.e., [¹¹C]-raclopride) (Shotbolt et al., 2012). As such, [¹¹C]-PHNO constitutes an optimal tracer for our proposed studies evaluating the effects of calcitriol on stimulant-induced DA release in humans. In addition, our group has considerable experience conducting such experiments with dextro-amphetamine challenges and [¹¹C]-PHNO in humans.

[¹¹C]-PHNO has been approved by the RDRC for use in previous human PET protocols at the Yale University PET Center. In addition, an IND was submitted to the FDA for the use of [¹¹C]-PHNO in another protocol at the Yale University PET Center. This IND was approved. We will add current protocol to that IND and we will also submit current protocol for approval by the Yale University RSC.

Calcitriol: The active form of vitamin D₃ is approved for the treatment of hypocalcemia in patients on chronic renal dialysis, hypocalcemia in hypoparathyroidism/pseudohypoparathyroidism, vitamin D resistant rickets, and secondary hyperparathyroidism in patients with moderate to severe chronic kidney disease not yet on dialysis. Another approved indication is psoriasis (e.g., topically). An off-label use is Vitamin D-dependent rickets type 1/pseudovitamin D deficiency rickets (PDDR). There have been phase I and phase II clinical studies on calcitriol for cancer (Beer, Munar et al. 2001, Beer, Javle et al. 2007, Beer, Ryan et al. 2007, Ramnath, Daignault-Newton et al. 2013). In terms of the oral administration, calcitriol comes in capsules of 0.5 mcg. The US labeling recommends doses up to 1 mg per day (e.g., for hypocalcemia in patients on chronic renal dialysis) or up to 2 mcg per day (e.g.,

for hypocalcemia in hypoparathyroidism/pseudohypoparathyroidism). To the best of our knowledge, calcitriol has never been tested/used in human subjects as an adjunct to stimulant medications.

Dextro-amphetamine (Dexedrine): Is a centrally acting sympathomimetic amine that promote release of catecholamines (primarily dopamine and norepinephrine) from their storage sites in the presynaptic nerve terminals. Another mechanism includes its ability to block the reuptake of catecholamines. It has been approved for treatment of Narcolepsy (e.g., doses up to 60 mg per day) and Attention Deficit Hyperactivity Disorder (ADHD) (e.g., doses up to 40 mg per day). It comes in tablets of 5, 7.5, 10, 15, 20, and 30 mg.

Radiotracer, calcitriol, and Dexedrine will be the same for ADHD subjects.

All protocols which utilize a drug, biologic or radiotracer **not** approved by, but regulated by, the FDA, or a radiotracer regulated by the RDRC, must provide the following information:

- a. What is the Investigational New Drug (IND) **number** assigned by the FDA?
- b. IND # for ¹¹C-PHNO is 134,138
- c. Who holds the IND?

Yale University PET Imaging Center

- c. All protocols which utilize a radiotracer not approved by, but regulated by the FDA must provide the IND number: _____ 134,138 _____

Alternatively, use of the investigational radiotracer may be under RDRC/RSC oversight: (check if appropriate) _____

For all investigational radiotracers, attach a copy of the RDRC/RSC application (for radioisotopes used in the PET Center, PET Center personnel may complete this step)

Go to <http://rsc.med.yale.edu/login.asp?url=myApps.asp>. When you have logged in, complete the application and attach a copy to this submission.

Alternatively, an **exemption from IND filing requirements** may be sought for a clinical investigation of a drug product that is lawfully marketed in the United States. If there is no IND and an exemption is being sought, review the following categories and complete the category that applies (*and delete the inapplicable categories*):

Exempt Category 1 for the calcitriol and dextro-amphetamines

The clinical investigation of a drug product that is lawfully marketed in the United States can be exempt from IND regulations if all of the following are yes:

- i. The intention of the investigation is NOT to report to the FDA as a well-controlled study in support of a new indication for use or to be used to support any other significant change in the labeling for the drug. Yes No
- ii. The drug that is undergoing investigation is lawfully marketed as a prescription drug product, and the intention of the investigation is NOT to support a significant change in the advertising for the product. Yes No
- iii. The investigation does NOT involve a route of administration or dosage level or use in populations or other factor that significantly increases the risks (or decreases the acceptability of the risks)

associated with the use of the drug product. Yes No

iv. The investigation will be conducted in compliance with the requirements for institutional (HIC) review and with the requirements for informed consent of the FDA regulations (21 CFR Part 50 and 21 CFR Part 56). Yes No

v. The investigation will be conducted in compliance with the requirements regarding promotion and charging for investigational drugs. Yes No

Exempt Category 2 (all items i, ii, and iii must be checked to grant a category 2 exemption)

i. The clinical investigation is for an *in vitro* diagnostic biological product that involves one or more of the following (check all that apply):

- Blood grouping serum
- Reagent red blood cells
- Anti-human globulin

ii. The diagnostic test is intended to be used in a diagnostic procedure that confirms the diagnosis made by another, medically established, diagnostic product or procedure; and

iii. The diagnostic test is shipped in compliance with 21 CFR §312.160.

Exempt Category 3

The drug is intended solely for tests in vitro or in laboratory research animals if shipped in accordance with 21 CFR 312.60

Exempt Category 4

A clinical investigation involving use of a placebo if the investigation does not otherwise require submission of an IND.

Background Information: Provide a description of previous human use, known risks, and data addressing dosage(s), interval(s), route(s) of administration, and any other factors that might influence risks. If this is the first time this drug is being administered to humans, include relevant data on animal models.

[¹¹C]-PHNO has been used in several PET centers (Ginovart, Willeit et al. 2007). It was initially developed at the PET Center, University of Toronto, and the safety of its use in humans has been demonstrated.

[¹¹C]-PHNO has been used extensively used in many clinical trials. A survey of the *ClinicalTrials.gov* website shows 12 completed trials, 5 recruiting trials, and 1 active clinical trial with [¹¹C]-PHNO investigating a variety of behaviors and disorders: alcohol drinking, addictive behavior, behavioral symptoms, cocaine-related disorders, compulsive behavior, depression, depressive disorder, drinking behavior, impulsive behavior, mental disorders, mood disorders, obsessive-compulsive disorder, psychotic disorders, schizophrenia studies, schizophrenia spectrum

and other psychotic disorders, psychological stress, substance-related disorders, and tobacco use disorder.

The use of [¹¹C]-PHNO in PET imaging in human was first reported in 2006 (Willeit, Ginovart et al. 2006). No relevant abnormalities in blood pressure, heart rate, or ECG were reported at any time in the study. There also were no relevant findings in physical or neurological exams or in routine blood and urine analyses during the study. However nausea was reported approximately 2–3 min after tracer injection, which subsided rapidly 2–3 min later. This effect was attributed to the transient high [¹¹C]-PHNO concentration resulting from the bolus injection (Willeit, Ginovart et al. 2006).

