Specific Aim 2: To determine whether acute calcitriol (vs. placebo) pre-treatment is associated with better performance on a test of attention (e.g., the continuous Performance Task or CPT–IP), after treatment with amphetamine. **Hypothesis:** We hypothesize that healthy human subjects pre-treated with calcitriol will have faster reaction times/higher accuracy on the CPT–IP vs. subjects pre-treated with placebo, after treatment with amphetamine.

Specific Aim 3: As part of a within-subject, two-days, study design, to determine whether acute calcitriol (vs. placebo) pre-treatment is associated with greater amphetamine (Amp)-induced dopamine (DA) release in the caudate, putamen, ventral striatum (VST), and substantia nigra / ventral tegmental area (SN/VTA) of subjects with attention deficit hyperactivity disorder (ADHD). **Hypothesis:** Similar to our hypothesis with healthy controls and congruent with our preliminary findings, we hypothesize that pre-treatment with calcitriol will produce greater Amp-induced DA release relative to placebo, resulting in lower post-Amp, [¹¹C]-PHNO BP_{ND} values on calcitriol as compared to placebo days.

Specific Aim 4: To determine whether acute calcitriol (vs. placebo) pre-treatment is associated with better performance on a test of attention (e.g., the continuous Performance Task or CPT–IP), after treatment with amphetamine. **Hypothesis:** Similar to our hypothesis with healthy controls and congruent with our preliminary findings, we hypothesize that individuals with ADHD pre-treated with calcitriol will have faster reaction times/higher accuracy on the CPT–IP vs. subjects pre-treated with placebo, after treatment with amphetamine
2. **Background:** Describe the background information that led to the plan for this project. Provide references to support the expectation of obtaining useful scientific data.

[figure not shown]

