amphetamine, subjects will have a second IV administration of up to 10 mCi of [¹¹C]-PHNO, followed by another 120-minute dynamic (i.e., emission and transmission) imaging session scan on a HRRT. Ninety minutes after starting the second [¹¹C]-PHNO scan, subjects will have blood drawn for the measurement of calcitriol, calcium (Ca), and Phosphorus (P) levels. Upon completion of the second [¹¹C]-PHNO scan, subjects will complete the 20-minute CPT-IP a second time. A summary of procedures described above is provided in Table 1. End of the test day will be after subject has tolerated lunch and has been cleared by the study physician for discharge. The amount of blood drawn during each experiment day is less than 70 ml.

If participating as an outpatient, ADHD subjects study will follow the exact same study design and follow all of the same study procedures as healthy controls, but will take their prescribed stimulant medication, at their normal prescribed dose, in place of the dextro-amphetamine. These subjects will not be asked to discontinue their medication leading up to or throughout the study procedures.

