If participating as an inpatient, ADHD subjects will follow the same MRI procedures, study procedures night before each experiment day, and test day procedures, with the main variation being that they will be admitted to the CNRU while they complete those. The CNRU is an inpatient, research dedicated, research unit, staffed 24 X 7 with medical and nursing staff, where visitors are screening/restricted. Upon admission to CNRU, subjects will conduct admission procedures including medical and psychiatric examination, blood work for CBC with differential, comprehensive metabolic panel with TSH and serum pregnancy test, urinalysis, ECG, and urine toxicology. The total length of stay on the CNRU will be up to 3 weeks depending on days needed to complete 5 half lives off stimulant medications and depending on slots for PET imaging scan which will be scheduled at least 6 days apart from each other. The first days on the CNRU are meant to acclimatized to the inpatient environment. Congruent with inpatient study procedures: they will not need to receive study medication to take home after MRI; they don't need to have administration of study medication monitored by Skype/Facetime; compliance with dietary measurements before test days is supervised by staff from CNRU; and they will be returning from the PET Imaging Center back to the CNRU after completion of each test day.

Follow up: The day after completion of each test day, subjects will be asked to return to the CNRU for a blood draw in order to measure calcium levels. The amount of blood drawn will be less than 5 ml. The purpose of this procedure is to monitor the development of hypercalcemia as an adverse event. In addition, a study physician will interview subjects in order to assess any potential residual side effects relative to their pre-scan baseline. At the end of the first follow up visit, subjects will receive 3 capsules of the study medication (i.e., each capsule will have calcitriol 0.5 mcg or placebo) as well as another instruction sheet for the second experimental day. The second experimental day is the same as the first one.

ADHD outpatient subjects will complete the same follow up. Inpatient subjects, because they are residing on the CNRU during those days, don't need to receive either the study medication or instructions for the next experiment day, as part of their follow up.

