Vital Signs		✓		✓	- 75 min (Q 15 min thereafter until stable after end of Scan #2)	
Eye blink rate		✓		✓	-60 min	
PRLT**		✓		✓	-45 min	
Cardiac Monitoring (Rate & Rhythm)		✓		✓	- 15 min (and continuously thereafter until stable after Scan #2)	
[¹¹ C]-PHNO injection & PET Scan #1		✓		✓	0	- 5 hr
Blood Draw (Calcitriol)		✓		✓	+ 90 min	
CPT-IP***		✓		✓	+ 120 min	
Dexedrine Dose (0.3 mg/kg PO) or Prescription Stimulant		✓		✓		- 150 min
Blood Draw (Amphetamine)		✓		✓		- 90 min
Blood Draw (Amphetamine)		✓		✓		- 30 min
Eye blink rate		✓		✓		- 15 min
[¹¹ C]-PHNO injection & PET Scan #2		✓		✓		0
Blood Draw (Calcitriol, Ca, and P)		✓		✓		+ 90 min
CPT-IP***		✓		✓		+ 120 min

*Drug Effects Questionnaire and simplified Amphetamine Interview Rating Scale

**Probabilistic Reversal Learning Task

***Continuous Performance Task – IP

^ Table applies to both healthy controls and ADHD subjects

Vitamin D measurements: In the context of vitamin D deficiency, 1-25(OH)₂D₃ (calcitriol) serum level measurement has insignificant diagnostic value. Instead 25(OH)D₃ level (not the active form) is widely measured as a marker of body vitamin D status (Holick 2009). In our study we will measure 25(OH)D₃ serum levels once, as part of the screening procedures (below 12 ng/ml will be set as the threshold to diagnose vitamin D deficiency/exclude subjects from the study). We will use the IDS-iSYS autoanalyzer from Immunodiagnostic Systems, for the measurement of 25(OH)D₃. This assay is based on chemiluminescence technology (Boscato and Stuart 1988, Sempos et al. 2012, Thienpont, Stepman et al. 2012).

Once the screening is completed, our main focus will be 1-25(OH)₂D₃ measurements on each test day since we are pre-treating our subjects with calcitriol. There is conflicting evidence regarding the relationship between these two values worldwide (Need, Horowitz et al. 2000, Need, O'Loughlin et al. 2008). Serum calcitriol levels will be measured via IDS-iSYS 1,25-Dihydroxy Vitamin D kit (Hussein, Ibrahim et al. 2015) three times on each experimental day, once prior to calcitriol/placebo administration, and within 90 minutes of each [¹¹C]-PHNO scan.

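### ADHD outpatients take their own prescribed stimulant, so a whole-cohort ADHD result cannot be labelled amphetamine-induced: reword Aims 3 and 4 and report by agent taken

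*Combined protocol and SAP*

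**What the plan says.** **What ADHD subjects receive.** In Section V.3, ADHD outpatients "will take their prescribed stimulant medication, at their normal prescribed dose, in place of the dextro-amphetamine". The next sentence adds: "These subjects will not be asked to discontinue their medication leading up to or throughout the study procedures". Table 1, which is footnoted as covering both cohorts, lists the challenge as "Dexedrine Dose (0.3 mg/kg PO) or Prescription Stimulant". The Dosing paragraph repeats that outpatients use their own prescription and gives Dexedrine to ADHD subjects only where it applies. Section V.7 requires a verified stimulant prescription and names no drug class.

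ADHD inpatients follow the healthy-control test-day procedures, which use dextro-amphetamine. Their length of stay varies "depending on days needed to complete 5 half lives off stimulant medications", and Section V.7 requires them to be stimulant-free at scanning.

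**What the aims and analysis claim.** Aim 3 reads: "we hypothesize that pre-treatment with calcitriol will produce greater Amp-induced DA release relative to placebo". Aim 4 compares attention with that of subjects "pre-treated with placebo, after treatment with amphetamine". The main comparison in Section V.12 is the relative change in binding potential "elicited by calcitriol + Amp vs. placebo + Amp", by paired t-test or Wilcoxon signed-rank test. For the second cohort it says only: "Statistical analyses will be the same for subjects with ADHD".

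**Other places.** Section VI.A.6 (Use of Controlled Substances) has every subject receiving dextro-amphetamine. Section VI.A.1 says that Dexedrine is the same for ADHD subjects.

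**The concern.** The aims and the analysis name one challenge drug, while part of the ADHD cohort may take another. The protocol's own Background (Section V.2) treats the difference as pharmacologically relevant: it lists methylphenidate and amphetamine as reuptake blockers, but gives amphetamine as its example of a drug that also enhances release. An outpatient on methylphenidate would receive no amphetamine, yet could count towards a result reported as amphetamine-induced release or post-amphetamine attention.

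Section V.12 does not say whether the challenge types are pooled or shown apart. If that choice is left until the data are seen, the result may influence it.

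**Working it through.** **1. The two ADHD settings side by side**

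| | Inpatients | Outpatients |
|---|---|---|
| Challenge | Protocol dextro-amphetamine | Own prescribed stimulant, class not restricted |
| Dose | Protocol weight-based dose | Own usual dose |
| Before scanning | More than 5 half-lives off stimulants | Not asked to stop |
| Label in Aims 3/4 and Section V.12 | Amphetamine | Amphetamine |

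The label fits the first column. It fits the second only for outpatients whose prescription is an amphetamine. Protocol dextro-amphetamine versus own prescription coincides exactly with inpatient versus outpatient and with washed out versus continuing. The design therefore cannot separate these factors.

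**2. The plan's own figure**

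Inputs from Section V.12: d' = 0.59, power 0.80, two-sided alpha 0.05, paired test. Section V.5: 30 per cohort, with an unstated allowance for loss.

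- Normal approximation: n = ((1.960 + 0.842)/0.59)² ≈ 22.5.
- Noncentral t: power = P(T > t(0.975, n−1)), where T has n−1 degrees of freedom and noncentrality d√n. At d = 0.59 this gives 0.790 at n = 24, 0.808 at n = 25 and 0.878 at n = 30.

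So 0.59 corresponds to 24 to 25 evaluable subjects, a loss of 6/30 = 20% to 5/30 ≈ 17%. That loss rate is inferred; the plan does not state it. The figure applies to a cohort tested as one group.

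**3. Precision if results are shown by group**

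The documents give no inpatient/outpatient split and no mix of agents, so the sizes below 30 are assumptions. The confidence-interval half-width is t(0.975, n−1)/√n, in SD units of the paired difference.

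| n | Power at d = 0.59 | Detectable d at 80% power | 95% CI half-width |
|---|---|---|---|
| 30 | 0.878 | 0.53 | 0.37 |
| 20 | 0.707 | 0.66 | 0.47 |
| 15 | 0.566 | 0.78 | 0.55 |
| 10 | 0.385 | 1.00 | 0.72 |

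A group of 5, which is possible once outpatients are divided by agent, would have a detectable d of 1.68.

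**4. Stimulant state at the baseline scan**

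Table 1 places scan 1 at 5 hours (300 min) and the stimulant at 150 min before scan 2. The test-day stimulant therefore comes 300 − 150 = 150 min after the scan 1 injection. Any stimulant present at scan 1 would be left from earlier doses.

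Test days begin at about 8 am with a check of fasting since 11:59 pm, and scan 1 starts about two hours after the morning study medication. If the fast covers prescribed medication, there are roughly 10 hours without oral drug before scan 1. The protocol does not say whether it does. The stimulant-related blood draws in Table 1 measure amphetamine only, so they would not document exposure to another agent.

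**The case against.** The strongest reply is that little is broken. Each subject is their own control. The prescription is verified through the prescriber, the state monitoring programme and the dispensed bottle (Section V.8) and is continued as prescribed, so agent and dose should match on both days. Stable carry-over would also be present on both days. The protocol elsewhere states its purpose as augmenting stimulant-induced release (for example in the Dosing paragraph), which a pooled estimate serves, and Section V.12 presents the sample as, at a minimum, a source of effect-size estimates. All of this stands. It limits the point to what the ADHD estimate may be called and how it is broken down.

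Four stronger readings are tempting, and the documents do not support them.

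- **The randomised comparison is biased or the sample size is wrong.** Neither is shown. For illustration, with 25 evaluable subjects, half of them outpatients, and equal SDs, pooled power would fall from 0.81 to 0.56 if the outpatient effect were half of 0.59, and to 0.27 if it were zero. Those outpatient effects are invented for the illustration; the documents give no basis for either.
- **Only Dexedrine-challenged subjects can inform an amphetamine conclusion.** A prescribed stimulant may itself be an amphetamine: the Background lists amphetamines among the common prescriptions, and Section VI.A.1 notes that dextro-amphetamine is approved for ADHD.
- **A difference between groups would show a drug difference.** Setting and washout are tied to the challenge, so it would not.
- **The plan commits to pooling.** That is the likely reading of the single sentence on ADHD, but it is an inference.

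**Conclusion.** The mismatch is real and should be fixed, but it is one of wording and reporting. A whole-cohort ADHD estimate is a valid calcitriol-placebo contrast averaged over agents, doses and baseline stimulant states. It supports a statement about stimulant-induced release and attention after a stimulant. It does not support an amphetamine-specific statement unless every subject received an amphetamine, which the protocol does not require.

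Validity of the contrast assumes the same agent and dose on both test days, which the protocol implies but does not state. The detectable effect of 0.59 is unchanged for the pooled analysis. Estimates by agent would be imprecise, and the size of that loss depends on a split that the documents do not give.

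Section VI.A.6 conflicts with the Research Plan, the Dosing paragraph and Table 1 on who receives dextro-amphetamine. Section VI.A.1 is only unclear, because the Dosing paragraph limits Dexedrine to the ADHD subjects to whom it applies.

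**What to change.** 1. In Aims 3 and 4 and Section V.12, word the pooled ADHD estimate as the effect of calcitriol on stimulant-induced dopamine release and on attention after a stimulant.
2. Replace the one-sentence ADHD provision in Section V.12 with text such as: *The same paired analysis will be applied to the ADHD cohort. Calcitriol-placebo estimates with 95% confidence intervals will also be given by agent actually taken: protocol dextro-amphetamine; prescribed amphetamine; methylphenidate or other. Amphetamine-specific conclusions will be drawn only from subjects who received an amphetamine, with the protocol dextro-amphetamine group also shown alone.*
3. Add the caveat: *Agent is confounded with inpatient or outpatient setting and with washout. Differences between groups are descriptive and will not be attributed to the drug. The groups are not powered.* Give the detectable effect per group under stated assumed sizes.
4. Record agent, dose and time of the last stimulant dose on each test day, and state whether the overnight fast covers prescribed medication. Agent and prescribed dose should already be available from the eligibility check.
5. Reconcile Section VI.A.6, and clarify Section VI.A.1, against the Research Plan, the Dosing paragraph and Table 1.

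The cost is wording and a few case-report fields, with no extra visits, scans, blood draws or assays. No fixed inpatient/outpatient split is required; that would be a recruitment commitment. The downside is lower precision in each group, and the amphetamine-specific part of Aims 3 and 4 may rest on few subjects if most take another agent.
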